# 😵 VHsquared

STATISTICAL ANALYSIS PLAN: PROTOCOL V56502 Page 23 of 40

### 15.1.2. MISSING DATA METHODS FOR PRIMARY EFFICACY VARIABLE

Missing responder will be defined if at any visit either CDAI score or CRP/FCP values are missing. The missing responder status will then be imputed.

Missing primary efficacy data will be imputed using a LOCF method based on the following criteria -

### 15.1.3. PRIMARY ANALYSIS OF PRIMARY EFFICACY VARIABLE(S)

The primary objective is to evaluate the efficacy of V565 555 mg TID in subjects with active CD measured by the

## 🕉 VHsquared

STATISTICAL ANALYSIS PLAN: PROTOCOL V56502 Page 24 of 40

proportion of subjects achieving response to therapy.

The primary efficacy analysis will be performed on ITT population. The primary endpoint will be analysed using a logistic regression model with treatment as the fixed effect and prior anti-TNF $\alpha$  therapy and baseline CDAI score as covariates. For the active treatment versus placebo comparison, the results will be presented in terms of an odds ratio together with its associated 95% CI and 2-sided p-value. Two-sided 95% CIs for the odds ratio will be provided.

The SAS® procedure GENMOD that will be used is given in appendix 3The CDAI score, FCP, CRP results along with the change from baseline values will also be listed and summarised for the ITT population.

### 15.1.4. SENSITIVITY ANALYSIS OF PRIMARY EFFICACY VARIABLE

The same primary efficacy analysis logistic regression model will be repeated using LOCF and WOCF on the ITT population.

The same primary efficacy analysis logistic regression model used for the ITT population will be repeated on the PP population. The same model used for primary efficacy will be used.

### **15.2.** SECONDARY EFFICACY

The secondary efficacy analyses will be performed and also be listed on ITT population.

### 15.2.1. SECONDARY EFFICACY VARIABLES & DERIVATIONS

The secondary efficacy variables are

Where subject achieving >=100 point reduction of CDAI score from baseline and a reduction of >=50% from the baseline value of CRP or FCP

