### 8.2.2 Secondary Efficacy Analyses

The secondary endpoints below will be analysed using the same model as used in the primary endpoint analysis.

- Proportion of subjects achieving a ≥100-point reduction in CDAI score and a concomitant reduction of 50% in CRP or FCP at Day 42
- Proportion of subjects achieving a  $\geq$ 70-point reduction in CDAI score at Day 42
- Proportion of subjects achieving a  $\geq$ 100-point reduction in CDAI score at Day 42
- Proportion of subjects achieving a CDAI score of <150 CDAI at Day 42

For the PRO-2 score assessments, the changes in total scores from Baseline to Day 14 and Day 42 will be analysed using a Mixed Model for Repeated Measures (MMRM) with treatment as the fixed effect, prior anti-TNF $\alpha$  and baseline scores as covariates.

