### **3.3.** CHANGES TO ANALYSIS FROM PROTOCOL

In the protocol section 8.2.1 it is mentioned that the baseline CRP and baseline FCP results will be included as covariates in the statistical model for logistic regression. CRP or FCP will be used to determine inflammation status at baseline. Some subjects may appear 'normal' on the basis of their CRP result however the FCP measurement reveals the presence of inflammation. As FCP will be measured for subjects only if CRP is <5 mg/L, FCP will be missing for many subjects. In addition, the CRP result for subjects who entered on the basis of inflammation measured by a FCP result => 250 ug/g will not be meaningful as a reflection of inflammation status. For these reasons neither FCP nor CRP will be incorporated into the primary model fit. However, if a subject is enrolled in the study based on the baseline result of FCP the definition of response will incorporate a 40% reduction in CRP. If a subject is enrolled in the study based on the baseline result of FCP the definition of response will incorporate a 40% reduction in CRP.

STATISTICAL ANALYSIS PLAN: PROTOCOL V56502 Page 12 of 40

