#### 15. **EFFICACY OUTCOMES**

#### 15.1. **PRIMARY EFFICACY**

#### 15.1.1. **PRIMARY EFFICACY VARIABLE & DERIVATIONS**

The primary efficacy variable is Responders at Day 42

A Responder is defined as subjects achieving both CDAI ≥70-point reduction from Baseline OR CDAI score <150, and a reduction of  $\geq$ 40% from the baseline value of CRP (where CRP at baseline => 5mg/dL) or FCP (where CRP at baseline <5mg/dL and FCP at baseline =>250 ug/g)

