### **15.3.** EXPLORATORY EFFICACY

### 15.3.1. EXPLORATORY VARIABLES & DERIVATIONS

15.3.1.1. Proportion of subjects achieving CRP or FCP levels within protocol defined normal limits at Day 14 and Day 42

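### The composite secondary endpoint (CDAI fall of at least 100 points plus a 50% marker fall) omits the qualifying-marker condition of the primary, so FCP-qualified subjects could meet it on a CRP that was normal at entry

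*SAP*

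**What the plan says.** **Secondary endpoint.** Protocol 8.2.2 asks for a CDAI fall of at least 100 points with a "concomitant reduction of 50% in CRP or FCP at Day 42". SAP 15.2.1 repeats this as "a reduction of >=50% from the baseline value of CRP or FCP". Neither says which marker applies to which subject.

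**Primary endpoint.** SAP 15.1.1 does say. The 40% fall is judged on "CRP (where CRP at baseline => 5mg/dL") or on "FCP (where CRP at baseline <5mg/dL and FCP at baseline =>250 ug/g"), so each subject has one marker.

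**What carries over.** Protocol 8.2.2 applies the primary model to the secondary endpoints, and SAP 15.2.2 applies the primary imputation. No visible text applies the marker condition.

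**Who has which marker.** Protocol 6.1.3 restricts FCP after screening to subjects whose screening CRP was below 5 mg/L and who qualified on FCP. It places no such restriction on CRP.

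**The SAP's own view of that CRP.** SAP 3.3 states: "CRP result for subjects who entered on the basis of inflammation measured by a FCP result => 250 ug/g will not be meaningful". The sense is that it does not show whether such a subject is inflamed, and the section gives this as one reason for leaving both markers out of the primary model.

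**The concern.** Read literally, the secondary gives FCP-qualified subjects two ways to satisfy the marker half and CRP-qualified subjects one. The extra way is a change in a CRP that was already below the entry threshold, where a fall from 3.0 to 1.4 mg/L counts as a response.

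Two things are at stake. First, this endpoint reads as the more demanding version of the primary: 100 points exceeds 70 and 50% exceeds 40%. With the same marker in both, every subject who met it would also meet the primary. With either marker allowed, that need not be so. Second, chance responses added to both arms pull the odds ratio, which is the plan's effect measure, towards 1.

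**Working it through.** No figure stated in the plan bears on this point, so there is none to reproduce. The check has three parts.

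**1. A worked FCP-qualified subject** (invented values, cut-off read as 5 mg/L)

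- CDAI 320 to 210: fall of 110.
- CRP 3.0 to 1.4 mg/L: (3.0 − 1.4)/3.0 = 53% fall.
- FCP 600 to 600 µg/g: 0% fall.

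| Rule | Marker judged | Result |
|---|---|---|
| Secondary as written (15.2.1) | CRP or FCP | met: 110 ≥ 100 and 53% ≥ 50% |
| Secondary on qualifying marker | FCP | not met: 0% < 50% |
| Primary under SAP 15.1.1 | FCP | not met: 0% < 40% |
| Primary under the protocol's unrestricted wording | CRP or FCP | met |
| Primary under the literal sentences in SAP 3.3 | CRP | met |

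**2. Nesting.** In 200,000 randomly generated profiles, 7,013 met the secondary as written and failed the 15.1.1 primary; all were necessarily FCP-qualified. With the secondary tied to the qualifying marker, the count was 0. This is a check of logic. The profiles were not drawn from a realistic population, so 7,013 says nothing about expected frequency.

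**3. Size.** The inputs below are assumptions; the documents give none of them.

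With no true change and no selection, the chance of a CRP fall of 50% or more is Φ(ln 0.5 / (√2 × s)), where s is the within-subject SD of log CRP. However, FCP-qualified subjects were selected for a CRP below 5 mg/L, so their next value tends to be higher. I simulated selection on an observed baseline below 5 mg/L, with between-subject log SD 0.8 to 1.1 and median CRP 5 to 10 mg/L before selection:

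| s | No selection | Selected on CRP < 5 mg/L |
|---|---|---|
| 0.3 | 5% | 2–4% |
| 0.45 | 14% | 5–9% |
| 0.7 | 24% | 8–15% |

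The last column is the relevant one. To see what it does to the endpoint, assume further:

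- CDAI response (100 points) of 30% on placebo and 45% on V565;
- qualifying-marker response among CDAI responders of 25% and 50%;
- a share f of 20% to 40% FCP-qualified;
- a chance CRP fall, with probability q, that is independent of CDAI and FCP.

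Tied to the qualifying marker: placebo 0.30 × 0.25 = 7.5%; V565 0.45 × 0.50 = 22.5%; odds ratio (0.225/0.775)/(0.075/0.925) = 3.58.

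Extra responders as written: placebo f × 0.30 × 0.75 × q; V565 f × 0.45 × 0.50 × q. Both equal f × 0.225 × q.

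- q = 0.02, f = 0.20: adds 0.09 points; 7.59% against 22.59%; odds ratio 3.55.
- q = 0.15, f = 0.40: adds 1.35 points; 8.85% against 23.85%; odds ratio 3.23.

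With these inputs the additions happen to be equal in the two arms, so the risk difference stays at 15 points and only the odds ratio shrinks.

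**The case against.** The strongest reply is that CRP or FCP is shorthand used throughout. The protocol states the primary endpoint in the same unrestricted words, and SAP 15.1.1 then shows that one marker per subject is meant. SAP 10 likewise reports baseline CRP for those qualifying on CRP and baseline FCP for those qualifying on FCP. Parts of SAP 15 are also missing from the public text, so a general convention may have stood there. This may well be the intention. It does not settle the matter, because the visible secondary definition omits a condition that the SAP writes out elsewhere, and a programmer following it would code either marker.

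A reader might go further in three ways that the documents do not support.

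- **That such subjects fail the primary whatever rule is used.** This holds under 15.1.1. SAP 3.3 says twice that subjects enrolled on FCP are judged on a 40% fall in CRP; under that sentence, anyone meeting the secondary on CRP also meets the primary. It looks like a drafting slip, since it conflicts with 15.1.1 and with the same section's view of that CRP, but it stands in the text.
- **That the exploratory normalisation endpoint is met by every FCP-qualified subject at entry.** Its title in SAP 15.3.1.1 ("Proportion of subjects achieving CRP or FCP levels within protocol defined normal limits at Day 14", and Day 42) has the same wording, but its derivation is not visible, so no defect can be asserted.
- **That chance CRP falls reach 24%.** That figure ignores selection on a low CRP.

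The schedule of events is not in the public text either, so Day 42 CRP in FCP-qualified subjects is inferred from Protocol 6.1.3.

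**Conclusion.** The point holds as a defect in one written definition. The visible text of SAP 15.2.1.1 does not carry over the marker condition of 15.1.1. As written, it lets FCP-qualified subjects with a Day 42 CRP respond on a value that the SAP itself regards as uninformative. Under 15.1.1, the secondary is then not a subset of the primary.

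The effect is probably a small dilution. The chance rate of about 2% to 15% applies to the marker half only, in FCP-qualified subjects only. It counts only when the subject also has the 100-point CDAI fall and has not already met the FCP criterion. In the illustration the odds ratio moves from 3.58 to between 3.55 and 3.23. All of this rests on assumed variances, response rates and FCP share, and on no true CRP change. The primary analysis under 15.1.1 is unaffected, and this is one of several secondary endpoints tested without multiplicity adjustment (SAP 7.4).

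**What to change.** 1. In SAP 15.2.1.1, replace the marker clause with: a reduction of ≥50% from baseline in the marker on which the subject qualified, as in 15.1.1 (CRP if baseline CRP ≥5 mg/L; FCP if baseline CRP <5 mg/L and FCP ≥250 µg/g).
2. Reconcile the two SAP 3.3 sentences that assign FCP-enrolled subjects to a CRP reduction with 15.1.1.
3. Reconcile the CRP unit: 15.1.1 prints mg/dL where eligibility uses mg/L, a tenfold difference (5 mg/dL = 50 mg/L). Do this before the rule is copied.
4. For 15.3.1.1, confirm that the derivation uses the qualifying marker; no rewrite is asked for.

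The cost is two or three SAP sentences and a program change, to be made before unblinding, and possibly a slightly lower response rate on this endpoint.

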## 🞖 VHsquared

STATISTICAL ANALYSIS PLAN: PROTOCOL V56502 Page 25 of 40

Where subject achieving >=70 point reduction of CDAI score from baseline

Where subject achieving >=70 point reduction of CDAI score from baseline

Where subject's CDAI score at day 42 is < 150

- the total PRO-2 score is extracted from selected subject-reported variables of the CDAI included in the subject diary
- PRO-2 will be calculated at Day 14 and 42

### 15.2.2. MISSING DATA METHODS FOR SECONDARY EFFICACY VARIABLE(S)

Imputation of secondary efficacy variables will also follow the same procedure as primary efficacy variables.

## 😵 VHsquared

STATISTICAL ANALYSIS PLAN: PROTOCOL V56502 Page 26 of 40

### **15.3.** EXPLORATORY EFFICACY

### 15.3.1. EXPLORATORY VARIABLES & DERIVATIONS

15.3.1.1. Proportion of subjects achieving CRP or FCP levels within protocol defined normal limits at Day 14 and Day 42

15.3.1.2. Changes from Baseline in CDAI score over time

- CDAI score is calculated at baseline, Day 14 and Day 42 as defined in the section 15.1.1
- Change from baseline at Day 14 and 42 are calculated using the formula mentioned in section 6.7

15.3.1.3. Changes from Baseline in CRP or FCP levels over time

• Change from baseline at Day 14 and 42 are calculated using the formula mentioned in section 6.7

# % VHsquared

STATISTICAL ANALYSIS PLAN: PROTOCOL V56502 Page 27 of 40

15.3.1.7. Changes in Endoscopic Mucosal Appearance – endoscopic sub study patients only

• Change from baseline at Day 42 in overall Mucosal Appearance assessed as Markedly Better, Slightly Better, No Difference, Slightly Worse, Markedly Worse, Cannot be Determined

15.3.1.8. Changes in Endoscopic Score for Crohn's Disease (SES-CD) – endoscopic sub study patients only

• Change from baseline in SES-CD at day 42 for the subjects with an SES-CD ≥7, or ≥4 if only the ileum is involved using the formula mentioned in section 6.7

### **15.3.2.** MISSING DATA METHODS FOR EXPLORATORY VARIABLE(S)

Imputation of secondary efficacy variables will also follow the same procedure as primary efficacy variables.

STATISTICAL ANALYSIS PLAN: PROTOCOL V56502 Page 28 of 40

### **15.3.3.** ANALYSIS OF EXPLORATORY VARIABLES

- 15.3.3.1. The proportion of subjects achieving CRP (or FCP) levels within protocol defined normal limits at Day 14 and Day 42
- will be summarised using frequency and percentage and listed by subject for the ITT population
- 15.3.3.2. The endpoints evaluating changes in CDAI score over time and changes in CRP (or FCP) results over time
- will be summarised using descriptive statistics and listed by subject for the ITT population

15.3.3.6. Overall mucosal appearance

• The number and proportion of subjects in each of the categories defined in section 15.3.1.8 will be summarised for each treatment group at Day 42

15.3.3.7. Change from baseline of SES-CD

will be summarised using descriptive statistics at Day 42

Page 29 of 40

### **16.** PHARMACOKINETIC ANALYSIS

Individual PK serum blood sample collection dates/times, and the associated V565 concentrations will be listed by visit for each subject.

The PK urine sample collection dates/times and V565 excreted will be listed by visit for each subject. The amount excreted will be determined as V565 concentration × urine volume of the urine sample at the visit.

Serum and urine V565 concentrations will be summarized using descriptive statistics by visit on the PK population.

### **17.** SAFETY OUTCOMES

All outputs for safety outcomes will be based on the Safety Analysis Set.

There will be no statistical comparisons between the treatment groups for safety data.

### **17.1.** Adverse Events

Adverse Events (AEs) will be coded using MedDRA Version 19.1.

Treatment emergent adverse events (TEAEs) are defined as:

1. A new event that occurs during or after treatment with study drug or

2. Any event present at Baseline that worsens in either intensity or frequency after exposure to study drug.

Page 30 of 40

### 17.1.1. ALL TEAEs

Incidence of TEAEs will be presented by System Organ Class (SOC) and Preferred Term (PT) and also broken down further by maximum severity and relationship to study drug.

### 17.1.2. TEAEs Leading to Discontinuation of Study Drug

For TEAEs leading to discontinuation of study drug, summaries of incidence rates (frequencies, percentages and events) by SOC and PT will be prepared.

### 17.1.3. SERIOUS ADVERSE EVENTS

Serious adverse events (SAEs) are those events recorded as "Serious" on the Adverse Events page of the eCRF. A summary of serious TEAEs by SOC and PT will be prepared.

### 17.1.4. Adverse Events Leading to Death

TEAEs leading to Death are those events which are recorded as "Fatal" on the Adverse Events page of the eCRF. A summary of TEAEs leading to death by SOC and PT will be prepared.

### **17.2.** LABORATORY EVALUATIONS

Results from the central laboratory will be included in the reporting of this study for Haematology, Chemistry and Urinalysis. All laboratory assessments will be included in the outputs.

Presentations will use SI Units.

Page 31 of 40

#### 17.3. **ECG EVALUATIONS**

Results from the Electrocardiogram (ECG) as collected from eCRF will be included in the reporting of this study.

# 😵 VHsquared

STATISTICAL ANALYSIS PLAN: PROTOCOL V56502 Page 32 of 40

### **17.4.** VITAL SIGNS

The following Vital Signs measurements as collected from eCRF will be reported for this study on SAF population:

- Systolic Blood Pressure (mmHg)
- Diastolic Blood Pressure (mmHg)
- Heart Rate (beats/min)
- Body Temperature (°C)
- Weight (kg)
- BMI (kg/m^2)

### **17.5.** PHYSICAL EXAMINATION

Physical examination findings as collected in eCRF and abnormalities associated, along with clinical significance will be tabulated and presented in the listings on SAF population.

# 😵 VHsquared

STATISTICAL ANALYSIS PLAN: PROTOCOL V56502 Page 33 of 40

### **17.6.** OTHER SAFETY ASSESSMENTS

- The serum pregnancy test performed at Screening and a urine pregnancy test at Day 1, Day 42 (the end of the study) and at Day 56 (the Follow-up Visit) or ET visit will only be listed on SAF population
- The safety parameters Activated partial thromboplastin time, the Serology laboratory assessments (Hepatitis B surface antigen, Hepatitis B surface antibody, Hepatitis B core total antibody, Hepatitis C antibody), C. difficile toxin and presence of other enteric, pathogens and QuantiFERON-TB Gold Test collected at screening visit as collected in eCRF will only be listed on SAF population
- The Pharmacogenetics sample data as collected in eCRF will only be listed on SAF population
- Titre values for anti drug antibodies for will be listed for all subjects both V565 and placebo at Day 1 (pre dose) and for V565 subjects only at Days, 14, 42 and 56. Results will be listed for each subject by visit and treatment on SAF population. Subjects who test positive for anti- drug antibodies will be tested to confirm whether the antibodies are neutralising.

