#### 3.1.4 Exploratory Objectives

The exploratory objectives are to:

- To assess the proportion of subjects achieving CRP or FCP levels within normal limits
- To assess changes in CDAI scores and CRP or FCP levels over time
- To determine changes in anti-V565 antibody titre

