### 6.4 Immunogenicity

Blood samples will be evaluated for the presence of anti-V565 antibody at the time points indicated in . Samples will be collected, labelled, stored, and shipped as detailed in the Central Laboratory Manual. Samples will be processed by LG(

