### 8.2.3 Exploratory Analyses

The exploratory endpoint evaluating the proportion of subjects achieving CRP (or FCP) levels within normal limits at Day 14 and Day 42 will be summarised using frequency and percentage.

The endpoints evaluating changes in CDAI score over time and changes in CRP (or FCP) results over time will be summarised using descriptive statistics.

The anti-V565 antibody responses will be summarised and listed for the safety (SAF) population.

In the exploratory endoscopy substudy, changes in the central reader's overall assessment and changes in SES-CD from Baseline to Day 42 will be summarised using descriptive statistics. Summary statistics presentation will be separated for subjects with ileum and colon involvement and for subjects with only ileal mucosal lesions.

Any additional analyses or data presentation details will be described in the SAP.

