### 8.2.7 Analysis Populations

Intent-to-Treat (ITT) population: The ITT population will include all randomised subjects. In this population, treatment will be assigned based upon the treatment arm to which subjects were randomised regardless of which treatment they actually received.

Per Protocol population (PP): The PP population will include all subjects who do not have major protocol violations that would affect the evaluation of the primary efficacy endpoint.

Safety population (SAF): The SAF population will include all randomised subjects who receive at least one dose of study drug. In this population, treatment will be assigned based upon the treatment subjects actually received, regardless of the treatment to which they were randomised.

Pharmacokinetic population (PK): The PK population will include all subjects in the SAF population who receive at least one dose of study drug and who have at least one post dose sample of serum and urine who do not have events or protocol deviations with the potential to affect PK concentrations.

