### 5.6. **IMMUNOGENICITY POPULATION**

The immunogenicity population will include all subjects in the SAF population who receive at least one capsule of V565/placebo and who have at least one pre dose sample of serum and who do not have events or protocol deviations with the potential to affect immunogenicity.

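### SAP 17.6 reports antibody titres after Day 1 for V565 subjects only, an undeclared departure from Protocol 8.2.3 that removes the concurrent placebo rate of new positives

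*SAP*

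**What the plan says.** Protocol 3.1.4 sets the exploratory objective: "To determine changes in anti-V565 antibody titre". Protocol 6.4 describes the sampling without limiting it to one arm: "Blood samples will be evaluated for the presence of anti-V565 antibody at the time points" given in the Schedule of Events. Protocol 8.2.3 fixes the output: "The anti-V565 antibody responses will be summarised and listed for the safety (SAF) population". Protocol 8.2.7 makes that a two-arm population: "The SAF population will include all randomised subjects who receive at least one dose of study drug".

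SAP 17.6 narrows this. Titres are to be listed "for all subjects both V565 and placebo at Day 1 (pre dose) and for V565 subjects only at Days, 14, 42 and 56". It then adds: "Results will be listed for each subject by visit and treatment on SAF population". No antibody summary appears there or elsewhere in the available SAP text. SAP 3.3 deals only with the CRP and FCP covariates and the response definition. SAP 5.6 defines a separate immunogenicity population, but 17.6 reports on the safety population.

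**The concern.** Two things differ between the documents: the arms reported after Day 1, and the type of output. Neither difference is declared.

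The first matters more. A V565 subject who is negative at Day 1 and positive at Day 42 may have responded to the drug. The result may also be assay background, or a low-level reactivity that moves above and below the cut-point. The placebo arm, sampled at the same visits and tested on the same assay, shows how often this happens without drug. With that arm left out after Day 1, every background conversion that is reported appears in the V565 column.

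Protocol 2.1 calls immunogenicity a major issue for the systemic anti-TNF products and presents low expected immunogenicity as a possible advantage of V565. The omission could therefore count against the product.

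**Working it through.** **Comparison of the texts**

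| Item | Protocol | SAP 17.6 |
|---|---|---|
| Arms at Day 1 pre-dose | Both (8.2.3 with 8.2.7) | Both |
| Arms at Days 14, 42, 56 | No arm limit in 6.4 or 8.2.3 | V565 only |
| Output | Summary and listing | Listing; no summary stated |
| Population | Safety | Safety; the 5.6 population is not used |
| Declared in SAP 3.3 | n/a | No |

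**Denominators.** Protocol 5.6 plans 84 V565 and 42 placebo subjects. The synopsis expects 114 completers (76:38) at 10% dropout. Check: 126 × 0.9 = 113.4, 84 × 0.9 = 75.6 and 42 × 0.9 = 37.8, which agree after rounding up.

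**Spurious new positives in the V565 arm.** The documents give no background rate, so p per sample is assumed. There are three post-dose samples. The result depends on how samples from one subject are related.

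- *Independent samples (upper end).* The chance of at least one post-dose positive is 1 − (1 − p)³.
  - p = 5%: 1 − 0.95³ = 14.3%; 0.1426 × 84 = 12.0 subjects.
  - p = 1%: 1 − 0.99³ = 2.97%; 0.0297 × 84 = 2.5 subjects.
  - Requiring a negative Day 1 sample multiplies by (1 − p): 12.0 × 0.95 = 11.4 and 2.5 × 0.99 = 2.5. With 76 completers in place of 84, the 5% figure before that step is 0.1426 × 76 = 10.8.
- *Fully persistent reactivity (lower end).* The same subjects are positive at every visit, including Day 1: 84 × 0.05 = 4.2, or 84 × 0.01 = 0.8. None is newly positive, so the count is 0.

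The range is thus about 0 to about 12 at 5%, and about 0 to 2 or 3 at 1%. It covers new positives only. Titre rises in subjects already positive are not counted.

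**What the placebo rate would add.** Suppose 8 of 76 V565 completers are positive at one visit: 10.5%, exact 95% interval 4.7% to 19.7%. Fisher's exact test is used here only as a gauge of how the reading changes.

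| Placebo positives | Rate | Two-sided p |
|---|---|---|
| 0/38 | 0% | 0.050 |
| 2/38 | 5.3% | 0.49 |
| 4/38 | 10.5% | 1.00 |

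The same V565 count reads quite differently depending on a rate that 17.6 does not report. The placebo arm is small: with 0 of 38 positive, the exact 95% upper limit is 1 − 0.025^(1/38) = 9.3%. It would bound the background rate loosely, but it would bound it.

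**The case against.** The case for leaving 17.6 alone has several parts, and some of them stand.

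- **Within-subject baseline.** The objective is a change in titre, and Day 1 titres are kept in both arms. Pre-existing reactivity can be seen in about 126 subjects, and each V565 subject has a baseline. Positives are also tested for neutralising activity. This stands. A reader might infer that the trial can say nothing about background; that goes too far. Only the concurrent rate of conversion without drug is missing.
- **SAP 5.6.** A reader might infer that 17.6 contradicts the immunogenicity population because that population includes placebo. It does not. Membership requires that subjects "receive at least one capsule of V565/placebo and who have at least one pre dose sample of serum", and 17.6 lists Day 1 pre-dose titres for placebo. The loose end is only that 17.6 does not use the population that 5.6 defines.
- **A summary may exist.** SAP 8 refers to table and listing templates that are not among the documents. Other bullets in 17.6 restrict output to listings with the word only; the antibody bullet lacks it. So a summary is not expressly ruled out. But a template that follows 17.6 would still have no post-dose placebo titres.
- **Placebo samples may not exist.** The Schedule of Events is not in the available text. Collection in both arms is likely, since Protocol 6.4 sets no arm limit and the study is double-blind, but it is not confirmed.
- **Weight.** The output is exploratory, and SAP 17 plans no statistical comparison of safety data between arms. No formal test is displaced. A descriptive column for the placebo arm remains useful.

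**Conclusion.** The discrepancy is real and limited. SAP 17.6 drops the placebo arm after Day 1, while Protocol 8.2.3 covers the whole safety population, and SAP 3.3 does not declare the change. The absence of a summary is firm for the available text and open for the templates. The loss is the placebo rate of new positives or titre rises over Days 14 to 56.

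Its size cannot be fixed from the documents. Spurious new V565 positives run from about 0 to about 12 of 84 at an assumed 5% background, and from about 0 to 2 or 3 at 1%. The upper figures need independent samples and all 84 subjects sampled at all three visits. A reader might take 12 of 84 as the expected number of false signals; the documents support neither the rate nor the independence.

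The point should be corrected before unblinding. It does not touch the primary analysis.

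**What to change.** 1. Amend SAP 17.6 to list titres for both arms at Day 1 pre-dose and at Days 14, 42 and 56.
2. Add one descriptive table by arm and visit: number and percent positive, number newly positive or with increased titre versus Day 1, and neutralising status. No test is needed.
3. State whether the safety population or the SAP 5.6 immunogenicity population is used.
4. If placebo post-dose samples are not drawn or will not be assayed, declare and justify the V565-only rule in SAP 3.3.

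The cost is SAP wording and one table. If placebo samples exist but were not going to be tested, assaying them all is an optional extra of up to 42 × 3 = 126 assays, or 38 × 3 = 114 on planned completers.
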